## **CASCADE STUDY**

**14**

Version 1.1 09/27/2017

## **INFORMED CONSENT**

This research will request the Institutional Review Board to waive documentation of informed consent.

## **BENEFITS**

Data generated from this retrospective study will be used in the design of a prospective study on central venous catheter care and management.

## **CONFIDENTIALITY**

Data will be handled in a confidential manner to meet mandated Information Technology (IT) security standards and prevent loss of privacy. All electronic files will be stored in an encrypted and password-protected database on a secure medical center server. Any research data extracted from participants' medical records will be recorded in REDCap and electronic spreadsheets will be kept on a password protected computer. The information will be de-identified for study analysis. If the results of the trial are published, participants' identities will remain confidential. Publication resulting from this research will not contain any information that could potentially identify participants either directly or indirectly.

## **DATA ANALYSIS**

The summary of the demographic characteristics will be presented. Continuous variables will be summarized using mean (SD) or median (interquartile range) depending on whether or not the data follow the normal distribution. Categorical variables will be summarized by frequency (percentage). Correlational analysis will be performed utilizing Pearson Correlation. Comparison of continuous variables between any independent groups will be examined using two-sided T-test or two-sided Wilcoxon rank sum test, analysis of variance (ANOVA) or Kruskal-Wallis test followed by pairwise tests, as appropriate. Categorical variables will be

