## **PRIMARY OBJECTIVE**

1. To explore the association between mechanical/technical, thrombotic, and other adverse outcomes associated with CVCs, PICCs and HD catheters due to variation in insertion and management practices and with adherence to hospital approved EBP guidelines for CVCs, PICCs and HD catheters.

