## **PRIMARY ENDPOINTS**

1. To document number of mechanical/technical, thrombotic, and other adverse outcomes associated with CVCs, PICCs and HD catheters in two groups:
  - 1a. Clinicians interventions and management in adherence with hospital approved EBP guidelines for CVCs, PICCs and HD catheters.
  - 1b. Clinicians interventions and management not in adherence with hospital approved EBP guidelines for CVCs, PICCs and HD catheters.

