## **STUDY DESIGN**

This is a single site retrospective (non-experimental) study utilizing the electronic medical record, both descriptive and correlational methods.

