## **CASCADE STUDY**

examined using Fisher's exact test or Pearson's Chi-square test, as appropriate.

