
## Appendix C

### CASCADE STUDY DATA COLLECTION TOOL

| Please provide in this format: |            |             |     | Not in this format: |            |                          |     |
|--------------------------------|------------|-------------|-----|---------------------|------------|--------------------------|-----|
| MRN                            | HAR        | Medication  | ... | MRN                 | HAR        | Medication               | ... |
| 1234567                        | 2000000001 | Albuterol   | ... | 1234567             | 2000000001 | Albuterol
Simvastatin | ..  |
| 1234567                        | 2000000001 | Simvastatin | ... |                     |            |                          |     |

| Item  | Values/examples   | Description  |
|---|---|--|
| MRN   | 7 or 9 digit number   | Patient's MRN  |
| HAR   | 10 digit number   | Patient's HAR  |
| Name  | XXX, XXX alphanumeric   | Patient full name  |
| Sex   | Male/Female   | Patient's gender   |
| Age   | Number  | Patient's age at admission (number)  |
| Line, Drain, Airway, Tubes and Wound (LDAW) of the following types: CVC, PICC and PIV             | Include only the following: CVC Double Lumen, CVC Single Lumen, Peripheral IV, PICC Double Lumen, PICC single lumen, PICC Triple Lumen                                  | Specifies the type of LDAW that was placed   |
| Date of LDAW placement  | XX/XX/XXXX X:XX:XX AM/PM  | The date and time the LDAW was placed  |
| Date of LDAW removal  | XX/XX/XXXX X:XX:XX AM/PM  | The date and time the LDAW was removed   |
| Calculated field:
Duration of LDAW  | Number of hours   | This can be calculated by subtracting the LDAW placement date from the LDAW removal date. Please present results to hours.   |
| LDAW Removal Reason   | Discharge, Catheter damage, therapy complete, leaking, occluded, per order, per protocol, purulent drainage, removed by patient, infiltrated, phlebitis, site change, other (comment) | The reason that the LDAW was removed   |
| Calculated field:
Unit in which the LDAW was placed                                     | Any hospital unit name  | This unit can be determined based on the following criteria: the time of LDAW placement falls between admission into this unit AND before transferred out of or is discharged from this unit.  |

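### Correlations are fixed as Pearson with no rank alternative, although the same paragraph allows for non-normal data everywhere else; a cheap improvement of low severity

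*Combined protocol and SAP*

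**What the plan says.** The Study Design section describes a retrospective study using "both descriptive and correlational methods". For correlation, the Data Analysis section has one sentence: "Correlational analysis will be performed utilizing Pearson Correlation". It names no pairs of variables, sets no normality condition and offers no other coefficient.

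The sentences around it are more flexible. Continuous variables are summarised by mean or median "depending on whether or not the data follow the normal distribution". Groups are compared on continuous variables by "two-sided T-test or two-sided Wilcoxon rank sum test, analysis of variance (ANOVA) or Kruskal-Wallis test followed by pairwise tests, as appropriate". Categorical variables are "examined using Fisher's exact test or Pearson's Chi-square test, as appropriate".

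The primary objective is "To explore the association between mechanical/technical, thrombotic, and other adverse outcomes" and practice variation or guideline adherence. The primary endpoint is "To document number of mechanical/technical, thrombotic, and other adverse outcomes associated with CVCs, PICCs and HD catheters in two groups", the groups being adherent and non-adherent management.

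The quantitative fields include the number of insertion attempts (Catheter Insertion list), the number of adverse outcomes (Primary Endpoints) and line duration. Appendix C derives duration as removal minus placement, with the instruction "Please present results to hours".

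**The concern.** The plan foresees non-normal data and provides for it in summaries and group tests, but not in correlation. That is an inconsistency within one paragraph.

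The variables make it relevant. Dwell time cannot be negative, and Background and Significance describes intended use running from days for non-tunneled lines to years for tunneled ones. Attempts and complication counts are small whole numbers with a floor. Right skew is therefore likely, though nowhere documented.

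Two things are at stake where both variables in a pair are skewed. Pearson can miss a monotone association that a rank coefficient would detect. And one extreme record, for example a line with a wrongly entered removal date, can determine the coefficient. The Limitations section itself warns of uneven documentation quality. The results are meant to feed the design of a prospective study, so a missed or spurious correlation could carry forward.

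**Working it through.** **Figures in the plan.** There is no power calculation to reproduce. The sample is a convenience sample of 175 CVC + 75 PICC + 50 HD = 300 records. No alpha, power, target correlation or distribution is stated. I use 50, 75, 175 and 300 as sample sizes; everything else below is assumed.

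**Assumptions.** Two-sided alpha 0.05. Two standard normal variables with latent correlation 0.3 are transformed to hours = exp(s × z), with log-SD s, and to negative binomial counts (mean 0.5, size 0.5). Each coefficient is tested with t = r × √((n − 2)/(1 − r²)) on n − 2 degrees of freedom; for Spearman, r is computed on ranks.

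**Step 1. Skewed hours with counts.** Power from 3,000 simulated datasets per cell (Monte Carlo error up to about 1.96 × √(0.25/3000) = 1.8 points):

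| n | Mild skew (s = 0.5): Pearson / Spearman | Strong skew (s = 1.2): Pearson / Spearman |
|---|---|---|
| 50 | 38% / 37% | 32% / 37% |
| 75 | 51% / 53% | 40% / 52% |
| 175 | 82% / 87% | 65% / 88% |
| 300 | 96% / 99% | 84% / 98% |

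Repeat runs agree within that error. At s = 1.2 and n = 175, a separate run gave 65.4% against 87.5%, a gap of 22.1 points. At s = 0.5 and n = 50 the two methods are close to level, with Pearson at most about 2 points ahead.

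**Step 2. The price if both variables are normal.** With 6,000 runs, Pearson / Spearman is 93.8% / 91.5% at n = 300 (correlation 0.2), 75.5% / 70.9% at n = 75 (correlation 0.3) and 58.0% / 52.6% at n = 50 (correlation 0.3). Spearman costs about 2 to 5 points.

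**Step 3. Yes/no pairs.** For two binary variables Pearson's coefficient is phi, and n × phi² equals the uncorrected chi-square statistic: 0.679 and 0.679 in a simulated table of 300. Spearman gives the same coefficient, and simulated power was identical (48.5% and 48.5% at n = 300, correlation 0.2). Nothing is lost.

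**Step 4. False positives.** For two independent log-normal variables, Pearson's rejection rate stayed between 3.9% and 5.6%, so skew alone did not inflate it.

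**Step 5. One extreme record.** Take independent log-normal variables with log-SD 1 and set one record to exp(3.5) = 33 times the median on both. Pearson was significant in 100% of 3,000 runs at n = 50 and again at n = 300. Spearman was significant in 5.8% and 5.3%.

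**The case against.** The strongest reply is that the main comparison does not depend on this sentence. The primary endpoint is a comparison of two groups, and Wilcoxon, Kruskal-Wallis, Fisher and chi-square are all planned. That is correct. A reader might infer that the primary endpoint is compromised; the documents do not support that.

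A reader might also infer that the many yes/no items will be handled badly. They will not: the plan sends categorical variables to Fisher or chi-square, and Pearson on two binary variables is phi in any case.

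Third, the size rests on assumed distributions and on a pair the plan never names. This also stands. No passage says that dwell hours will be correlated with complication counts. Dwell is also time at risk, so that pair is arguably a question about rates, which Spearman does not answer either. The power loss is therefore a range, and one end of it is about nil.

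Fourth, the outlier effect was shown with a planted record, not with data from this hospital. It shows what can happen, not how often.

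None of these replies explains why correlation alone is given no alternative in a paragraph that allows for non-normality twice.

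**Conclusion.** The point holds in a limited form. Pearson is prescribed unconditionally for correlations while the surrounding text anticipates non-normal data. The consequence is confined to correlations between two quantitative variables, and the plan does not say which these are.

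Under the assumptions above (latent correlation 0.3, two-sided alpha 0.05, log-normal hours with over-dispersed counts), Pearson's power relative to Spearman's runs from about 2 points higher (log-SD 0.5, n = 50) to about 22 points lower (log-SD 1.2, n = 175). A single record extreme on both variables can produce significance by itself. It would go too far to say that the variables are known to be skewed, or that skew by itself raises the false-positive rate.

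This is a cheap improvement of low severity: the objective is exploratory, and neither an alpha level nor a target correlation is set.

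**What to change.** Replace the correlation sentence in Data Analysis with one that does three things before any data are analysed:

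- names the pairs of variables to be correlated;
- uses Spearman rank correlation with a 95% confidence interval for hours, counts and scores;
- keeps Pearson for pairs in which both variables are approximately normal.

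Yes/no pairs stay with the Fisher or chi-square tests already planned. Naming the pairs will also show whether any of them, such as dwell against event count, is really a question about rates.

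The cost is one sentence of text and an option in the SAS software already specified, with no new data. The downside is about 2 to 5 points of power for any pair analysed by ranks that is in fact normal on both sides.

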## **INCLUSION CRITERIA**

Adult patients in MICU, CCU, CSICU, SICU and hemodialysis with either CVCs, PICCs, or HD catheters.

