## **SAMPLE SIZE**

The total number of CVCs and PICCs inserted in MICU, CCU, CSICU, SICU in year 2015 and 2016 is summarized in Table 2 and Table 3 below:

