**Table 3- PICCs Inserted in Critical Care Units**

| PICC | 2015 | 2016 |
|-------------|-------------|-------------|
| MICU        | 32          | 10          |
| CCU         | 60          | 32          |
| CSICU       | 56          | 68          |
| SICU        | 44          | 56          |

A convenience sample of three-hundred medical records will be reviewed for this study, one-hundred and seventy-five CVCs, seventy-five PICCs, and fifty HD catheters representing 25%, 45% and 10% respectively of the total number of catheters inserted in 2016.

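### The unit of analysis is undefined and nothing handles repeat lines in one patient; if patients recur, the listed tests are not valid as written

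*Combined protocol and SAP*

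**What the plan says.** The combined protocol and SAP uses three different units.

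- **Patients.** Inclusion Criteria admits "Adult patients in MICU, CCU, CSICU, SICU and hemodialysis with either CVCs, PICCs, or HD catheters".
- **Catheters.** Sample Size builds its frame from "The total number of CVCs and PICCs inserted in MICU, CCU, CSICU, SICU in year 2015 and 2016" (Tables 2 and 3). These are insertions, not people.
- **Records.** Below Table 3 the sample is given as "A convenience sample of three-hundred medical records will be reviewed for this study, one-hundred and seventy-five CVCs, seventy-five PICCs, and fifty HD catheters". The plan does not say whether a record is a patient, an admission or a line.

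The extract in Appendix C is at line level. Under an MRN and a HAR it holds the field described as "Specifies the type of LDAW that was placed" and, for each line, "The date and time the LDAW was placed", with removal time, duration and removal reason.

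For analysis, the plan names Pearson correlation, and for continuous variables "Comparison of continuous variables between any independent groups will be examined using two-sided T-test or two-sided Wilcoxon rank sum test", with ANOVA or Kruskal-Wallis as further options. The closing sentence of Data Analysis gives Fisher's exact or Pearson's chi-square for categorical variables. That sentence governs a comparison of complications, yes or no, between the adherent and non-adherent groups in Primary Endpoints. No section sets a one-line-per-patient rule, an index-catheter rule or a method for clustered data.

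**The concern.** Every listed test treats each row as independent of the others. Two lines in one patient are likely to share severity of illness, unit, staff and charting habits, so their outcomes may be correlated. If the same patient supplies several rows, the test's error rate need no longer be the nominal one. Appendix C lists occlusion, catheter damage and site change among the removal reasons, and a further line is plausible after any of these.

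The results are meant to inform a prospective study (Benefits). A misstated strength of association would carry into its design. Timing also matters: Confidentiality says identifiers are removed before analysis. Without a coded patient key, repeat lines could not be recognised afterwards.

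**Working it through.** **1. The plan's own figure.** 175 + 75 + 50 = 300 catheters, and 300 records are planned, so the mean is 300/300 = 1.0 catheter per record. The total reproduces. It fits one line per record, but does not show that each record is a different patient.

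**2. Inputs the documents do not give.** Lines per patient (m), within-patient correlation (ICC) and the significance level are not stated. Assumed here: m from 1 to 2, ICC from 0.1 to 0.5, two-sided 5%.

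**3. Adherence the same for all of a patient's lines.**

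- Design effect: DE = 1 + (m − 1) × ICC
- Effective sample size: 300/DE
- True two-sided error: 2 × [1 − Φ(1.96/√DE)]

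Each cell shows DE; effective n; true error.

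| m | ICC 0.1 | ICC 0.3 | ICC 0.5 |
|---|---|---|---|
| 1 | 1.000; 300; 5.0% | 1.000; 300; 5.0% | 1.000; 300; 5.0% |
| 1.25 | 1.025; 293; 5.3% | 1.075; 279; 5.9% | 1.125; 267; 6.5% |
| 1.5 | 1.050; 286; 5.6% | 1.150; 261; 6.8% | 1.250; 240; 8.0% |
| 2 | 1.100; 273; 6.2% | 1.300; 231; 8.6% | 1.500; 200; 11.0% |

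This formula assumes equal numbers of lines per patient, which a mean of 1.25 cannot give. With unequal numbers, m is replaced by Σm²/Σm. If 75% of patients have one line and 25% have two, that is (0.75 × 1 + 0.25 × 4)/1.25 = 1.4. At ICC 0.1, DE = 1.04 and the error is 5.5% rather than 5.3%. The picture does not change.

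**4. Adherence not shared within a patient.** The table above covers one case only. A simulation of Pearson's chi-square on 300 lines (assumed complication risk 20%, beta-binomial within patient, 20,000 runs per setting) gave these true error rates:

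| Patients with two lines | Distinct patients | ICC | Adherence shared by a patient's lines | Adherence independent by line | Adherence opposite on a patient's two lines |
|---|---|---|---|---|---|
| 30 | 270 | 0.1 | 5.2% | 5.1% | 4.8% |
| 75 | 225 | 0.3 | 6.8% | 4.9% | 3.6% |
| 150 | 150 | 0.5 | 10.9% | 5.0% | 0.6% |

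The Monte Carlo standard error near 5% is √(0.05 × 0.95/20,000) = 0.15 percentage points. The shared column agrees with the formula: with 75 pairs, Σm²/Σm = (150 × 1 + 75 × 4)/300 = 1.5, so DE at ICC 0.3 is 1.15 and the error is 6.8%.

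**The case against.** The best reply is that the plan already implies one line per patient: 300 records equal 300 catheters, and the inclusion wording suggests that a patient has one type of line or another. On that reading the design effect is 1 and nothing is wrong. The reading is possible, but it is nowhere stated, and a frame of insertions lets the same person appear again through another line or admission.

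Appendix C is also weaker evidence than it looks. Its example with a repeated MRN concerns medications, each on its own row. Its list of lines includes peripheral IVs and omits HD catheters, so the extract is not the analysis set. It shows that line-level rows will exist, not that patients will recur among the 300.

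The phrase about independent groups in Data Analysis does not settle the matter. Separate groups do not make the rows within each group independent, and a patient with one line in each group would make the groups themselves dependent. The Fisher and chi-square sentence carries no such phrase.

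A reader might infer that p-values will be too small. The documents do not support this. Primary Endpoints does not say whether adherence is classified per line, patient or clinician, and several recorded items (inserter, number of attempts, site, unit) belong to a single line. Where adherence differs between a patient's lines, the test is about nominal or conservative. A reader might also infer that confidence intervals will be too narrow, but the plan specifies none.

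Finally, the objectives are exploratory and Limitations already cautions about the design. That lowers the stakes, but does not supply the missing definition.

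**Conclusion.** The concern holds in conditional form. It is certain from the documents that the unit of analysis is undefined, that repeat lines or admissions are not excluded, and that every named test assumes independent observations. Whether this does harm depends on facts that the documents do not give.

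- One line per patient: no effect.
- Patients recur and adherence is shared within a patient: a nominal 5% test has a true error of about 5% to 11%, with effective n from 293 down to 200.
- Patients recur and adherence varies between lines: about nominal, falling to 0.6% in the most extreme setting simulated, which means lost power.

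These sizes rest on assumed values for lines per patient, ICC, complication risk and significance level. The low end is negligible. The claim that several lines per patient are planned, or that the results will be too optimistic, goes beyond what the documents say. The gap should still be closed, because closing it costs little and changes almost nothing if no patient recurs.

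**What to change.** Before abstraction, define *record* in Sample Size and state the unit at which adherence is classified. Then choose one of two routes.

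1. **One index catheter per patient**, for example the first eligible line in the study window, with a rule for patients who have lines of more than one type. The listed tests can then stand. The cost is that replacement lines are dropped, so the results describe first lines only, and some duplicate records must be replaced.
2. **Keep all lines** and compare groups with GEE or cluster-robust variance, clustering on patient. Because analysis data are de-identified, replace the MRN with a coded patient key rather than deleting it without a substitute. The cost is slightly more analysis work and possibly larger standard errors.

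Under either route, report the number of distinct patients beside the number of catheters. The change to the document is a few sentences in Sample Size and Data Analysis, plus one coded field in the dataset for the second route.

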## **CASCADE STUDY**

examined using Fisher's exact test or Pearson's Chi-square test, as appropriate.

## **DATA MANAGEMENT**

All data in this study will be obtained from multiple sources: EPIC and the Business Intelligence Department and review of clinician notes. REDCap will be utilized to for study data entry. All study data will be exported to Microsoft Excel for data analysis preparation, and imported for SAS version 9.4 (SAS Institute Inc. Cary, NC, USA) for data analysis.

## **LIMITATIONS**

A limitation in use of retrospective data collection from the patients medical record is incomplete and/or missing data related to variability in the quality and completeness of documentation by healthcare team members. In addition, because this is a single site study, the generalizability of the study's findings will be limited to the medical center. Also, the non-experimental design limits correlation between adherence to the guidelines and catheter success rate.

## Appendix A

Current Status: Active

PolicyStat ID: 1615811

Origination Date: 08/2010  
Approved: 10/2013  
Last Revised: 10/2013  
Next Review: 09/2016  
Owner: [name], Manager  
Policy Area: DOPC - Clinical Procedures  
Applies To:

### Apheresis Catheter Maintenance, A-2

#### Purpose

1. To outline the nursing management of patients with apheresis catheter/s.
2. To provide central access routes for apheresis, fluid and medication administration, blood transfusion/sampling and/or hyperalimentation.

